6.2 Objectives

General purpose:

To evaluate the safety and efficacy of the ophthalmic solution PRO-157 in three different posologies versus Moxifloxacin and versus Gatifloxacin in patients with bacterial conjunctivitis.

Specific objectives:

To determine the safety of the PRO-157 solution in three different posologies versus Moxifloxacin and versus Gatifloxacin in patients with bacterial conjunctivitis by the incidence of adverse events and visual capacity.

To evaluate the efficacy of the ophthalmic solution PRO-157 in three different posologies versus Moxifloxacin and versus Gatifloxacin in patients with bacterial conjunctivitis through conjunctival cul-de-sac culture and the clinical evaluation of some ocular signs and symptoms such as: burning, lacrimation, Foreign body sensation, pruritus, photophobia, conjunctival hyperemia, chemosis, secretion, palpebral edema, membranes and / or pseudomembranes, scales and epitheliopathy.

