• The safety of the use of PRO-157 will be evaluated in the visits indicated in the schedule, through the following parameters:

1. Visual capacity
2. Eye surface
3. Exploration of the previous segment
4. Exploration of the posterior segment
5. Burning
6. Foreign body sensation
7. Lachrymation
8. Conjunctival hyperemia
9. Itching
10. Photophobia
11. Chemosis
12. Tear discharge
13. Eyelid edema
14. Membranes / pseudomembranes
15. Scales
16. Corneal epithelial defects
17. Adverse events

It will be considered that the drug under evaluation is safe for use in humans if there are no changes in the parameters indicated in more than 5% of the subjects, in both eyes, if the

patient goes to all the visits of the study and complies with adherence to treatment $\geq 80\%$ during the time of evaluation of the study.

Variable	Operationalization	Measurement scale	Value
Visual ability	Independent Discrete quantitative	Points logMAR 0-1 0 = Snellen 20/20	Do not present change in 1 line in the Snellen letter or in 1 logarithmic point (log MAR)
Ocular surface	Dependent Qualitative ordinal	Absent Present	Abnormalities in any area of the ocular Surface
Exploration of the previous segment	Dependent Qualitative ordinal	Normal Abnormal	Abnormalities in any of the structures included: cornea, iris, pupil, irido-corneal and crystalline angle.
Exploration of the posterior segment	Dependent Qualitative ordinal	Normal Abnormal	Abnormalities in any of the structures included: vitreous, retina, macula and the optic nerve
burning	Dependent Qualitative ordinal	Absent Present	Must be recorded as absent in 95% of the subjects evaluated
strange body sensation	Dependent Qualitative ordinal	Absent Present	Must be recorded as absent in 95% of the subjects evaluated
tearing	Dependent Qualitative ordinal	Absent Present	Must be recorded as absent in 95% of the subjects evaluated

Secretion	Dependent Qualitative ordinal	Absent Present	Must be recorded as absent in 95% of the subjects evaluated
Conjunctival hyperemia	Dependent Qualitative ordinal	Absent Mild Moderate Severe	You must comply with the following: Absent ≥ 95.0% Mild ≤ 5.0% Moderate ≤ 2.5% Severe ≤ 1.0%
Photophobia	Dependent Qualitative ordinal	Absent Mild Moderate Severe	You must comply with the following: Absent ≥ 95.0% Mild ≤ 5.0% Moderate ≤ 2.5% Severe ≤ 1.0%
Chemosis	Dependent Qualitative ordinal	Absent Present	Must be recorded as absent in 95% of the subjects evaluated

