Eyelid edema	Dependent Qualitative ordinal	Absent Present	Must be recorded as absent in 95% of the subjects evaluated
Membranas Pseudomembranes	Dependent Qualitative ordinal	Absent Present	Must be recorded as absent in 95% of the subjects evaluated
Scales	Dependent Qualitative ordinal	Absent Present	Must be recorded as absent in 95% of the subjects evaluated

Epithelial defects corneal	Dependent Qualitative ordinal	Affected area, percentage	Percentage of the affected area 95%
Adverse events	Dependent Qualitative ordinal	serious Not Serious	Must be recorded as absent in 95% of the subjects evaluated

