18. VALUATION OF SECURITY

18.1 Safety measurements

Figure (8.2.2) 1 - Research Program indicates safety measurements that are made in each visit or treatment period.

Security criteria

- Adverse events and visual ability

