20.1 Events to be registered

An adverse event is defined as any unfavorable medical occurrence in a subject that is participating in a clinical trial, whether or not there is a causal relationship with the study drug and / or experimental procedures, that is present or detected as of the date that the patient signs the form of information and consent, regardless of the period of the study.

Therefore, the investigator will document as an adverse event:

- Any unfavorable and unintended sign, including an abnormal finding of an additional examination that the investigator considers clinically important,
- Any intercurrent symptoms or illness,
- Any worsening during the study of a symptom or disease already present when the patient entered the study (increase in frequency and / or intensity), and which:
 - It is detected during a study visit or in an additional examination,
 - Be present from the previous visit of the study and notify the patient.

A serious adverse event, that is, an event that, regardless of the dose of the study drug administered:

- How the patient's death results
- Be a threat to life,

Note: the term "threat to life" refers to an event in which the patient was at risk of death at the time of the event; it does not refer to an event that hypothetically could have caused death if it had been more serious.

- How persistent or important disability / disability results. Note: an event that seriously disrupts the patient's ability to lead a normal life, in other words that causes a significant change, deterioration, injury or alteration of the functions or body structure of the patient, physical activity and / or quality of life.
- Be a congenital anomaly / birth defect. Exposure to the study drug before conception (in man or woman) or during pregnancy that causes an adverse outcome in the child.

Note: any event that may not be an immediate threat to life or result in death or hospitalization but may endanger the patient or may require intervention to avoid one of these outcomes (eg, edema or allergic bronchospasm requiring treatment) intensive at home, blood dyscrasia, seizures that do not cause hospitalization, or development of drug dependence or drug abuse).

Consumption of the study drug by a person other than the patient:

- Minors: any consumption of the study drug with or without medical consequences must be notified immediately to the sponsor.

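### The adverse-event limit sets one all-cause 5% cap for serious and non-serious events together and makes no comparison with moxifloxacin or gatifloxacin

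*Combined protocol and SAP*

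**What the plan says.** Section 6.2 sets a safety objective for PRO-157 against moxifloxacin and gatifloxacin, to be judged "by the incidence of adverse events and visual capacity". The hypotheses in section 6.1 claim non-inferiority on safety as well as efficacy. Section 18.1 names the safety criteria as "Adverse events and visual ability".

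Section 7.1 turns this into a rule in two places:

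- The text lists 17 safety parameters, with adverse events as the last. It calls the drug safe "if there are no changes in the parameters indicated in more than 5% of the subjects, in both eyes", with the further condition that the "patient goes to all the visits of the study and complies with adherence to treatment" of at least 80%.
- The table that follows gives adverse events the scale "serious Not Serious" and one value for both categories: "Must be recorded as absent in 95% of the subjects evaluated".

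In the same table, hyperemia and photophobia have graded limits: mild at most 5.0%, moderate at most 2.5%, severe at most 1.0%.

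Section 20.1 defines an adverse event as any unfavourable occurrence "whether or not there is a causal relationship with the study drug and / or experimental procedures", and the list of what to document includes "Any intercurrent symptoms or illness". Collection runs to the telephone call on day 23. Section 21 has the investigator assess causality, but the limit in section 7.1 does not use that assessment.

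**The concern.** The plan has a pre-specified verdict on safety, and adverse events are one of its two named criteria. As worded, that criterion has three weaknesses.

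- **No separation by seriousness.** A subject with a serious event counts the same as a subject with a cold. The table does tighten its limits for worse grades of redness and light sensitivity.
- **No separation by cause.** Unrelated illness over about three weeks uses up the allowance.
- **No comparator.** An absolute cap cannot say whether PRO-157 is as safe as moxifloxacin or gatifloxacin, which is the question asked.

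Followed literally, the rule could count subjects with serious events as within limits, or mark down a harmless product for background illness. In neither case would it answer the stated objective.

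**Working it through.** **Inputs**

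- Limit: at least 95% of subjects without an event (section 7.1 table). This agrees with the 5% rule in the section 7.1 text.
- Group size: 60 eyes (section 1 and section 8).
- Eyes per subject: one or two, since section 8 takes the infected eye or eyes into account. So 60 eyes means 30 to 60 subjects per arm. The number of subjects is not stated.
- Event rate: none is given for this trial. Section 5 reports no adverse events in phase I, in healthy volunteers using four drops daily. The rates below are assumptions.

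**Step 1: the cap as a count.** The cap is the largest x with (n − x)/n ≥ 0.95.

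| Subjects n | Largest x that passes | Share without event at x | At x + 1 |
|---|---|---|---|
| 30 | 1 | 29/30 = 96.7% | 28/30 = 93.3% |
| 40 | 2 | 38/40 = 95.0% | 37/40 = 92.5% |
| 59 | 2 | 57/59 = 96.6% | 56/59 = 94.9% |
| 60 | 3 | 57/60 = 95.0% | 56/60 = 93.3% |
| 90 (three arms pooled, 30 each) | 4 | 86/90 = 95.6% | 85/90 = 94.4% |
| 180 (three arms pooled, 60 each) | 9 | 171/180 = 95.0% | 170/180 = 94.4% |

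Within one arm, three subjects with an event pass only if there are exactly 60 subjects. Four fail at every size from 30 to 60. In the pooled case four pass. The count is of subjects with an event, so several events in one subject count once.

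**Step 2: contrast within the table.** The 1.0% limit for severe hyperemia allows 0.01 × 60 = 0.6, that is, no subject out of 60. The adverse-event row allows 3 out of 60, and nothing prevents all three from being serious. Reading the 95% separately for each category changes nothing: three serious would still pass and four colds would still fail.

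**Step 3: chance that one arm fails this row.** P(fail) = P(X > cap), with X binomial(n, p) and p the true share of subjects with any event.

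For n = 60 and p = 0.05: P(X ≤ 3) = 0.046 + 0.145 + 0.226 + 0.230 = 0.647, so P(fail) = 0.353. For n = 30 and p = 0.05: P(X ≤ 1) = 0.215 + 0.339 = 0.554, so P(fail) = 0.446.

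| Assumed rate p | n = 60, cap 3 | n = 30, cap 1 |
|---|---|---|
| 1% | 0.003 | 0.036 |
| 2% | 0.032 | 0.121 |
| 5% | 0.353 | 0.446 |
| 10% | 0.863 | 0.816 |
| 15% | 0.985 | 0.952 |

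**Step 4: precision at the boundary.** The exact 95% interval for 3/60 is 1.0% to 13.9%. An arm that just meets the limit is therefore compatible with a true rate well above 5%.

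**The case against.** The strongest reply has four parts.

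*Serious events are handled elsewhere.* Section 20.1 defines them separately, section 20.3 follows events up, section 21 assesses cause, and Appendix 3 is an individual report form with seriousness criteria and a narrative. The contents also list a section 20.4 on serious events, whose text is not fully visible in the public copy. This stands as far as reporting goes, so one should not infer that the whole plan treats a serious event like a cold. But nothing in the visible text links that reporting to the verdict in section 7.1, which rests on the percentages.

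*The row is only one of 17.* This also stands. A reader might infer that three serious events in an arm are enough to call PRO-157 safe, but the documents do not support that. The other 16 parameters, attendance and adherence also apply, and a serious ocular event could breach the visual capacity, ocular surface or segment rows. The gap is clearest for a serious event that leaves those rows unchanged.

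*Four colds need not fail the drug.* This stands too. The rule names PRO-157 and does not say whether it applies per arm or to the three posologies together. Pooled, four subjects pass. Nor does the wording support the inference that the rule could declare a comparator unsafe.

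*Event rates may be low.* Phase I reported none, and at 1% or 2% an arm of 60 rarely fails. That is fair, but those were healthy volunteers. This trial enrols patients aged 0 to 99 years, counts any intercurrent illness and follows them to day 23.

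One might add that section 23 describes each variable in the intention-to-treat set and runs a bivariate analysis per protocol. That sentence names neither adverse events nor a comparison, and it does not replace the stated verdict.

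**Conclusion.** The concern holds in a limited form. The adverse-event limit is a single all-cause cap that ignores seriousness and cause and involves no comparator, while the objective and hypotheses are comparative. Followed as written, it can support a wrong safety conclusion.

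Its size depends on points the plan leaves open. Per arm, 1 to 3 subjects with an event are allowed, depending on how many subjects lie behind 60 eyes; pooled over PRO-157, 4 to 9. Up to that number, subjects with serious events meet this row. Per arm, four subjects with unrelated illness fail it at any size from 30 to 60. The chance that an arm fails runs from 0.3% to 98.5% with 60 subjects, and from 4% to 95% with 30, over assumed rates of 1% to 15%. The documents neither support nor exclude a particular rate in that range. The counts in Step 1 do not depend on it.

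**What to change.** - **Section 7.1, text and table together.** Remove adverse events from the parameters under the 5% rule and delete the 95% value from the adverse-event row. Deleting only the table value would leave the same cap in force through the text.
- **Safety conclusion.** State that serious adverse events are listed and assessed individually as part of the conclusion, with no percentage allowance.
- **Section 23.** Report by arm the per-patient incidence of all, ocular, and treatment-related adverse events, with the difference from each comparator and its 95% confidence interval. Use all treated patients, which is the intention-to-treat set already defined there, and state the number of subjects as the denominator. This also fits section 15.3, which keeps withdrawn subjects' data for safety. The attendance and adherence condition in section 7.1 should be reconciled with that section.

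The cost is a table row, an edit to the rule and a paragraph in section 23, using data already collected. The trial loses its single pass mark for adverse events. The intervals will be wide: with 5% in both arms, the half-width is about 1.96 × √(2 × 0.05 × 0.95/60) = 7.8 percentage points with 60 subjects per arm, and 11.0 with 30. The comparison should therefore be labelled descriptive.

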8 STUDY PLAN

This is a phase II, randomized, double masked, multicentre, national study.

This study will be carried out with 60 eyes with diagnosis of bacterial conjunctivitis, by treatment group, of patients of the ophthalmological consultation.

Patients diagnosed with bacterial conjunctivitis (signs and / or symptoms and / or culture) recruited will be treated for 7 days with any of the three posologies of PRO157, Moxifloxacin, or Gatifloxacin. The randomization of any of the medications will be coordinated by a member of the research team previously designated who will not be masked and will be responsible for indicating to the patients how to apply the drops, emphasizing the patients of by no means mentioning the evaluating physician with the frequency who applies the study medication.

No patient may use the aforementioned treatment more than the prescribed time. For purposes of the protocol, the infected eye (s) will be taken into account at baseline but the study medication and procedures will be applied and will always be done in both eyes to protect the healthy eye and the possibility of infection if Do not be infected from the beginning.

The study is divided into the following periods:

There will be a total of 3 visits which are divided into 1 baseline visit (day 1) 1 treatment visits (day 3), 1 final visit (day 8). A telephone call will finally be made to evaluate adverse events after 15 days of the last application of medication (day 23)

At each visit from the baseline a clinical photograph of the eyes will be made, each of them must be identified by patient and visit number and delivered once the 30 patients are completed on a CD or USB.

1. Period of treatment of 7 days (from day 1 to 7) where any of the following posologies are applied according to randomization:

PRO157 1 drop 2 times a day in both eyes.
PRO157 1 drop 3 times a day in both eyes.
PRO157 1 drop 4 times a day in both eyes.
Moxifloxacin 1 drop 3 times a day in both eyes
Gatifloxacin1 drop 3 times a day in both eyes

The study medications will be delivered by a coordinator (not blinded) or a person previously designated by the principal investigator, who will indicate how to apply the study medication according to the randomization and will place special emphasis on not mentioning the principal investigator or designee. perform the evaluations as the drop or any characteristic of the jars is applied.

An artificial lagrima without conservative Lagricel Ofteno® will also be applied one drop 4 times a day to all patients who enter the study during the 7 days of treatment with the study medication.

The valuation days indicated in Figure 1 of the Study Plan must be carefully observed. A variation of ± 1 days can be accepted in relation to the inclusion visit (from day 1 to 8). In the case of the inclusion of subjects from 0 years to less 18 years minus 1 day, they will be included progressively as follow:

- Age group of 12 to 18 years.
- Age group from 2 to 12 years old.
- Age group from 0 to 12 years old.

This with the intention of integrating patients once the dosage parameters have been established as safe and recommended for the younger age groups.

The indications of the inclusion periods will be made as the results are gathered in the groups of minors.

Blinding

The double-blind study is a procedure in which the patient and the attending physician do not know which of the intervention groups was assigned by the study patient. The blinding codes are protected by a person outside the study.

Figure 1 - Plan of the Study

[figure not shown]

Table 2: Timeline

Procedimiento	Visita Basal				
		Visita 1	Visita Final	Seguimiento Telefónico EA	Visita no programada / Descontinuación
	Día 1	Día 3	Día 8	Día 23	
Criterios de Elegibilidad	X				
Firma de consentimiento informado	X				
Datos demográficos	X				
Prueba de embarazo en orina (si aplica)	X		X		
Historia Clínica General y Oftalmológica	X				
Padecimiento actual					X
Toma de muestra para cultivo	X		X		
Fotografía clínica de los ojos	X	X	X		
Asignación de número al paciente	X				
Entrega de medicamento	X				
Inicio de aplicación de medicamento	X				
Aplicación de medicamento	X	X	X		
Devolución de medicamento por parte del paciente			X		
Sintomatología Ocular (A,B,C,D)	X	X	X		X
Agudeza y/o Capacidad Visual	X	X	X		X
Biomicroscopia anterior (F,G,H,I,J,K)	X	X	X		X
Tinciones de fluoresceína/verde de lisamina	X	X	X		
Revisión del segmento posterior (L,M,N,O)	X	X	X		X
Evaluación de eventos adversos	X	X	X	X	X
Evaluación de medicamentos concomitantes	X	X	X		X

A) Burning B) Lachrymation C) Foreign body sensation D) Pruritus E) Photophobia DF) Conjunctival hyperemia G) Chemosis H) Secretion I) Eyelid edema J) Membranes and / or pseudo-membranes K) Epitheliopathy L) Vitreous M) Retina N) macula O) optic nerve.

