Ha: The ophthalmic solution PRO-157 is so safe and effective in some of its different posologies when demonstrating non-inferiority when compared against Moxifloxacin and Gatifloxacin in the treatment of conjunctivitis	

Sponsor's name: Laboratorios Sophia, S.A. of C.V.

Finished Product Name: NA

Active Ingredient Name: Pazufloxacin

Methodology

Multicentric double randomized study masked.

Number of participants: 300 eyes, 60 eyes per treatment group

Diagnosis and main criteria for inclusion

Patients with bacterial conjunctivitis (signs and / or symptoms and / or culture)

Subjects aged 0 years to 99 years.

Study medication:

Pazufloxacin

- **Treatment duration:**
- - **Recruitment period: 4 months**
- - **Period of treatment: 7 days**
- - **Period of follow-up: 15 days**

Criteria for evaluation:

Efficacy measurements:

Main efficacy criterion

It will be determined as effective if there is a reduction in the number or species of bacterial flora comparing the basal culture against the final between the five different groups of patients and / or if there is a reduction or absence of the infection with the clinical evaluation through signs and symptoms such as: burning, tearing, foreign body sensation, pruritus,

photophobia, conjunctival hyperemia, chemosis, secretion, palpebral edema, membranes and / or pseudomembranes, palpebral scales and epitheliopathy

Security measurements:

Visual ability

Adverse events

INDICE

1. Summary of the study	2
2. Glossary and definitions	6
3. Administrative structure of the study	7
3.1 Parties not sponsored.	7
3.2 Sponsored parties	8
4. Background information	8
4.1 Justification	9
4.2 Non-clinical pharmacology	11
5. Clinical Studies	17
6. Hypothesis and Objectives	17
6.1 Work hypothesis	17
6.2 Objectives.	19
7. Point or points limit	19
8. Study plan	25
9. Measures to minimize deviations	29
10. Products administered	30
11. Description of the packaging	31
12. Management of the study medication	31
13. Closure of the center	33
13.1 Premature discontinuation of study	31
13.2 Center closure	31
14. Source data	33
15. Selection and withdrawal of subject of study	33
15.1 Inclusion criteria	33
15.2 Exclusion criteria	34
15.3 Criteria for patient withdrawal	36
16. Treatment of the study subjects	37
16.1 Managed treatments	37
16.2 Delivery of treatment	37
16.3 Previous and concomitant treatments	37
16.4 Treatments authorized during the study	39
16.5 Drug compliance	39
17. Methods and times of measurements	39

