16 TREATMENT OF STUDY SUBJECTS

16.1 Managed treatments

Lagricel Ofteno® Apply one drop 4 times a day for 7 days + any of the following according to the randomization in both eyes.

Apply one drop of PRO157, 2 TIMES a day, from day 1 to day 7
Apply one drop of PRO157, 3 TIMES a day, from day 1 to day 7
Apply one drop of PRO157, 4 TIMES a day, from day 1 to day 7
Apply a drop of Moxifloxacin, 3 TIMES a day, from day 1 to day 7
Apply a drop of Gatifloxacin, 3 TIMES a day, from day 1 to day 7

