18.2 Times of Measurements

Clinical examination

Basal visit (Day 1)

The principal investigator or the head of the research team of the site duly specified must obtain the letter of informed consent of each of the subjects, before carrying out any procedure of the study.

When the informed consent is obtained and all the inclusion criteria and none of exclusion are met, a unique identification number of the subject will be assigned, this will be used throughout the study for its identification.

Female subjects who are of reproductive age will be tested for pregnancy in urine.

The following evaluations will be made:

Signature of informed consent

Review of inclusion criteria and exclusion criteria,

Demographics,

Urine pregnancy test (if applicable),

General and ophthalmological clinical history,

Clinical Photography,

Sampling of conjunctival sac fundus for culture,

Assigning number to the subject,

Delivery of medication,

Ocular symptoms: burning, tearing, foreign body sensation, pruritus, photophobia

Visual acuity and / or visual ability,

Anterior biomicroscopy: Conjunctival hyperemia, chemosis, secretion, palpebral edema, membranes and / or pseudomembranes, scales, epitheliopathy,

Fluorescein staining,

Green stain of lysine,
Posterior segment revision: Retina, Macula, Vitreous and Optic nerve.
Evaluation of adverse events.

This day the patient will be included, if clinically it suggests a bacterial conjunctivitis, it will be randomized and at that same moment a clinical photograph of his eyes will be made and a sample will be taken for culture of both eyes, immediately he will go with the person previously designated to randomize him, this person will not be masked and will give specific instructions to the patient on how to apply the study medication and will remember the importance of the patient not mentioning the study's evaluating physician how many times the treatment is applied, then he will start with the study medication regardless of the crop results.

Treatment visits:**Visit 1 (Day 3)**

Between the days of study there may be a window of \pm 1 day. If for any reason an assessment is made on any day not planned in the study, this information should be recorded in the unscheduled visit format found within the FRC.

At each follow-up visit, an ophthalmological examination will be performed in order to evaluate the following parameters.

1. Acuity and / or Visual Ability
2. Clinical Photography,

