23. STATISTICS

Sample size

We conducted a review of published articles regarding the use of medications in the treatment of bacterial conjunctivitis. We found three publications that are the following:

- 1) "Gatifloxacin Ophthalmic Solution for Treatment of bacterial Conjunctivitis: Safety, Efficacy and Patient Perspective". Clyde Schultz. En Ophthalmology and Eye Diseases. 2012:4 65-70.
- 2) "Microbiological Efficacy of a New Ophthalmic Formulation of Moxifloxacin Dosed Twice-Daily for Bacterial Conjunctivitis". Shachar Tauber et.al. En Adv Ther. (2010) 28(7):566-574.
- 3) "Clinical use of gatifloxacin ophthalmic solution for treatment of bacterial conjunctivitis". Lorenzo J. Cervantes y Francis S. Mah. En Clinical Ophthalmology. 2011:5 495.502.

The first of the publications referred to here (Clyde Schultz) is a review article that summarizes the findings regarding the use of gatifloxacin mainly as a treatment for bacterial conjunctivitis but does not give precise figures, it only says, for example, that the Effectiveness reported in an article made in China was around 93%. It is not an original article that gives specific results, but rather comments findings and issues an opinion regarding the convenience of using them as an effective and safe treatment for bacterial conjunctivitis.

The second revised article (Schachar Tauber) is an original article. This is a multicentre study in which 1180 patients were recruited throughout the United States of America, who had a clinical diagnosis of bacterial conjunctivitis. All patients were given a sample

prior to treatment and another at the end of treatment, which were sent to the clinical laboratory where standard methods of microbiology were used to isolate the biological specimens before and after the treatments. One group was treated with MOXI-AF and the other with placebo (vehicle) instilling in the conjunctival sac one drop twice a day for three days and the most important results of this investigation are summarized in Table 1.

The third article reviewed (Cervantes) describes other studies conducted to test gatifloxacin in two presentations: Zymar (0.3%) tested in 52 patients treated for three days vs. placebo (vehicle) tested in 48 patients and Zymaxid (0.5%) tested in 333 patients for three days vs. placebo (vehicle) tested in 325 patients for three days.

The results reported in these articles regarding efficacy can be summarized in Table 1.

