conjunctivitis found in the articles reviewed between patients treated with any drug vs patients treated with placebo. The Fleiss formula is used for case-control studies.

From the calculations made we can draw the following conclusions and recommendations. The average absolute efficacy found in the articles commented is almost 70% (69.8%) for patients treated with any medication and only 53.3% for patients treated with placebo (in this case vehicle was used as a placebo). According to the Fleiss formula for cases and controls, a sample of 147 cases per group assures us that if the differences that we are going to prove between the treatments is of that magnitude (69.8 %% vs 53.3%) or greater, we will have a 80% probability that the statistical test that we apply to evaluate the differences will be statistically significant (Power or power of the sample), and on the other hand, if the differences between the treatments were not of that magnitude (the differences were of lesser magnitude), when applying a statistical test on the results of a sample of 147 cases with minor differences to the ones presented, it will be not significant and the probability of this happening will be 0.95 (Reliability of the sample).

In summary, to prove differences in the absolute efficacy of two treatments in which one has almost 70% absolute efficacy and the other of only 53.3%, a sample of 147 cases per group will be necessary to have a reliability of 95% and a 80% power.

If instead of calculating the sample size with absolute efficiency we calculate it with the specific efficacy for specific bacteria, using the percentages that we obtained from the review of the articles published and that were 92.34% and 66.12% for patients treated with some medication and for those treated with placebo respectively, the sample according to the Fleiss formula for a 95% reliability and a power of 80% is 44 patients per group.

We can suggest that the minimum sample should be 50 eyes per treatment group and if possible, it would be desirable that the sample per group could reach 150 cases per group.

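### The size is fixed at 60 eyes per arm but patients are randomised; with no study-eye or eye-combination rule, 60 eyes may be 30 to 60 patients, so the plan's own 44 per group is not assured

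*Combined protocol and SAP*

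**What the plan says.** The Summary gives the size as "Number of participants: 300 eyes, 60 eyes per treatment group", and Section 8 repeats it: "This study will be carried out with 60 eyes with diagnosis of bacterial conjunctivitis, by treatment group". Assignment is by patient. At the baseline visit (Section 18.2) the patient is examined and sampled in both eyes, and "immediately he will go with the person previously designated to randomize him". Section 16.1 then gives "any of the following according to the randomization in both eyes". On which eyes count, Section 8 says only that "the infected eye (s) will be taken into account at baseline".

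Section 23 mixes the units. It describes one source study as "Zymar (0.3%) tested in 52 patients treated for three days vs. placebo (vehicle) tested in 48 patients", while the table built from the same counts labels them as eyes. For specific efficacy it concludes that "the sample according to the Fleiss formula for a 95% reliability and a power of 80% is 44 patients per group", and the next paragraph recommends a minimum of 50 eyes per group with no conversion.

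The decision criteria in Section 7.1 are worded by patient (success) or by subject (the 95% limits and the safety rule). The analysis sets in Section 23 are sets of subjects. No section says which eye is the study eye, how two infected eyes become one patient result, or how correlation between eyes is handled. The only analysis named is a bivariate analysis in the per-protocol set. Section 8 also says that photographs are to be "delivered once the 30 patients are completed on a CD or USB", without saying whether the 30 refers to an arm, a site or something else.

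**The concern.** Two eyes of one patient share the host, often the pathogen, and always the assigned regimen. They carry less information than two patients. A formula for independent units gives a number of patients, or of eyes only if each patient contributes one. Reading its result as eyes, when a patient may contribute two, can leave fewer independent units than the formula requires.

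Two things are at stake. The first is the only link between the chosen 60 and a stated power, namely the 44 per group. The second is the meaning of the Section 7.1 criteria: they speak of patients and subjects, but a patient with one cleared and one uncleared eye has no defined result.

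**Working it through.** **Inputs from Section 23 and Annex 1:** P1 = 0.9234 and P2 = 0.6612 (specific efficacy, medication and placebo), two-sided alpha 0.05, power 80%, ratio 1:1. **From the Summary and Section 8:** 60 eyes per arm. **Assumed, because the documents give neither:** b, the share of patients with both eyes counted, 25% and 50%, with 100% as an extreme; rho, the inter-eye correlation, 0.3, 0.5 and 0.8.

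**Plan's own figure.** The Fleiss formula gives m' = 36.37 and, after the continuity correction, 43.7, so 44. This reproduces the plan. The companion calculation (69.8% vs 53.3%) gives m' = 135.27 and 147.1 after correction, against the stated 147.

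**Patients behind 60 eyes.** N = 60/(1+b): 60 at b = 0, 48 at 25%, 40 at 50%, 30 at 100%. N falls below 44 once b exceeds 60/44 − 1 = 36%.

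**Power at n units.** Inverting the correction with d = 0.9234 − 0.6612 = 0.2622 gives m' = (n − 1/d)²/n. Power is 92% at n = 60, 84% at 48, 80% at 44, 76% at 40 and 59% at 30.

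**Case A: all infected eyes analysed, GEE with exchangeable correlation.** With n_two = N·b and n_one = N − n_two, effective n = n_one + 2·n_two/(1+rho).

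| b | rho 0.3 | rho 0.5 | rho 0.8 |
|---|---|---|---|
| 25% (36 one-eye, 12 two-eye patients) | 54.5 | 52.0 | 49.3 |
| 50% (20 and 20) | 50.8 | 46.7 | 42.2 |
| 100% (0 and 30) | 46.2 | 40.0 | 33.3 |

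Power at these sizes is 89, 88, 86% (b = 25%); 87, 83, 78% (50%); 83, 76, 66% (100%).

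The 44 is missed at b = 50% only if 20 + 40/(1+rho) < 44, so rho > 0.67. At b = 100% it is missed if 60/(1+rho) < 44, so rho > 0.36. At b = 25% it is never missed, because even rho = 1 leaves 36 + 12 = 48. If each eye has equal weight instead, effective n is 60/DE with DE = (n_one + 2·n_two·(1+rho))/60, and the b = 50% threshold falls to about 0.55.

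**Case B: one eye per patient analysed.** If the 60 are recruited as eyes, both eyes fill the quota and one is then dropped, there are 48, 40 or 30 units at b = 25, 50 or 100%, with power 84, 76 or 59%. If one eye per patient is also the recruitment rule, 60 eyes are 60 patients, b is irrelevant and power is 92%.

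**Case C: one result per patient.** For a bilateral patient, P(both eyes clear) = p² + rho·p(1−p), and P(either clears) = 1 − [(1−p)² + rho·p(1−p)]. These are mixed with p for unilateral patients in proportion b. At b = 50% (40 patients) and rho = 0.3, 0.5, 0.8:
- both eyes must clear: power 86, 83, 79%
- either eye suffices: power 62, 66, 72%

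The missing rule alone moves power by 7 to 24 points.

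**The 95% limits.** Suppose 57 of 60 eyes are clear (95.0%) and b = 50%, so there are 40 patients. If two of the three failing eyes belong to one patient, 38/40 = 95.0% of patients are fully clear and the limit is met. If they belong to three patients, 37/40 = 92.5% and it is missed.

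**Only if eyes were tested as independent.** True two-sided error = 2(1 − Φ(1.96/√DE)). For rho 0.3 to 0.8, DE is 1.12 to 1.32 at b = 25%, giving 6.4 to 8.8%; at b = 50% it is 1.20 to 1.53, giving 7.4 to 11.3%.

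**The case against.** The plan uses eye and patient almost interchangeably: the Summary counts participants as eyes, and Section 23 gives the same literature counts as both. On that reading one eye per patient may be what is meant, and 60 eyes are then 60 patients with 92% power. This is possible and stays open. But no section says so, the wording on infected eyes allows two, and in the sponsor's own rabbit study (Section 4.2) 10 animals per group were analysed as 20 eyes.

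The 60 also leaves slack over 44. That stands as far as it goes: at 25% bilateral a clustered analysis always keeps 44, and at 50% it takes a fairly high correlation to lose it.

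The 44 is itself a weak benchmark. It is a drug-versus-placebo figure, none of the five arms is placebo, and the hypothesis is non-inferiority with no margin given. It serves here only because it is the plan's sole tie between its size and a stated power. The plan's other calculation asks for 147, and 60 independent units would give about 38% power for it, so clustering is not the main weakness of the sizing.

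A reader might go further in four ways that the documents do not support:
- That the arms will hold 30 patients, because Section 8 mentions 30 patients. That figure concerns delivery of photographs and its scope is not stated.
- That the unit is wholly unfixed. The criteria and analysis sets are written by patient or subject; what is missing is the step from eyes to patient.
- That the type I error is inflated. This needs an eye-level test, which the plan neither specifies nor excludes. With no margin, no false non-inferiority rate can be tied to the plan.
- That a result meeting the 95% limit by eye will miss it by patient. It can, but need not.

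**Conclusion.** The concern holds in this form: size is set in eyes, randomisation is by patient, and no rule connects the two, so the 80% power attached to 44 units is not assured. It is not shown to be lost. A shortfall depends on a bilateral share and a correlation that the documents do not give, and on which of the unstated analyses is used. Within the assumed ranges, effective size per arm runs from 33 (all bilateral, correlation 0.8) to 55, and 60 if the plan means one eye per patient throughout. The missing discordant-eye rule matters at least as much as the correlation, because it changes what a success is. All power figures refer to the plan's 92.34% vs 66.12% contrast and say nothing about non-inferiority power. This should be fixed before the data are seen, so that neither the eye rule nor the analysis is chosen with results in hand.

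**What to change.** In Sections 8 and 23, make the patient the unit of inference, in one of two ways:
- one study eye per patient by a preset rule, with the 60 then counted as patients; or
- all eyes infected at baseline, analysed by a method clustered on patient, for example GEE with a small-sample-corrected robust variance.

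In either case:
- State how a patient with one cleared and one uncleared eye counts.
- Put the Section 7.1 percentages on the patient unit.
- Restate the size as expected patients per arm, with effective n and power over a stated range of bilateral share and correlation.
- Say what the 30 patients in Section 8 refers to, or correct it.

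The cost is wording, slightly more analysis work and a less favourable stated precision. No new procedure is needed, and the restatement by itself calls for no added enrolment. The one-eye option discards second-eye data. If the sponsor had expected both eyes to fill the quota, counting the 60 as patients means 60 per arm where that quota would have given 48 (25% bilateral) or 40 (50%).
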